4 STATISTICAL ANALYSES

4.1 GENERAL CONSIDERATIONS

Continuous data will be summarized using the number of observations available, mean, standard deviation (SD), median, [Q1, Q3] minimum, and maximum. Categorical and ordinal data will be summarized using the count and percentage of participants.

All analyses will be presented on a single all participants group.

Observation period of the open-label extension study

The observation period will be divided into 4 segments:

- The **pre-treatment period** is defined as the period up to first investigational medicinal product (IMP) administration in the LTS15823 study.
- The **treatment-emergent (TE) period** is defined as the period from the first IMP administration in the LTS15823 study to the last IMP administration in the LTS15823 study +30 days. The treatment-emergent period includes the following 2 periods:
 - The **on-treatment period** is defined as the period from the first IMP administration to the last administration of the IMP +1 day.
 - The **residual treatment period** is defined as the period from the end of the ontreatment period to the end of the treatment-emergent period.
- The **post-treatment period** is defined as the period from the end of the treatmentemergent period.

The on-study period is defined as the time from enrollment until the end of the study defined as the last scheduled visit for those who completed the study and the end-of-study date collected on electronic case report form (e-CRF) page "Completion of End of Study" for those who did not complete the study. If death is the end-of-study reason, date of death will be used.

4.2 PARTICIPANT DISPOSITIONS

The number (%) of participants included in each of the analysis populations listed in Table 3 will be summarized.

Screen failures are defined as participants who consent to participate in the LTS15823 study but are not subsequently enrolled. The number (%) of screen failures and reasons for screen failures will be provided in the screened population.

The number (%) of participants in the following categories will be provided:

- Enrolled participants.
- Enrolled but not exposed participants.

- Enrolled and exposed participants.
- Participants who did not complete the study treatment period as per protocol and main reason for permanent intervention discontinuation.
- Participants who did not complete the study period as per protocol and main reason for study discontinuation.

Reasons for permanent study intervention and study discontinuation "adverse event" and "other reasons" will be split as related versus not related to Covid-19, if applicable.

The number (%) of exposed and not enrolled participants will also be summarized.

In addition, the number (%) of participants screened, screened-failed, enrolled, with permanent intervention discontinuation and with early study discontinuation will be provided by country and site.

Protocol deviations

Critical and major protocol deviations (automatic or manual) during the long-term extension open-label period will be summarized in the enrolled population, as well as displayed separately as related versus not related to Covid-19 if applicable.

4.3 PRIMARY ENDPOINT(S) ANALYSIS

Not done.

4.3.1 Definition of endpoint(s)

The primary endpoint of percent change in TKV based on MRI from the EFC15392 study baseline to 24 months of open-label extension study will not be analyzed.

4.3.2 Main analytical approach

Not applicable.

4.3.3 Sensitivity analysis

Not applicable.

4.3.4 Supplementary analyses

Not applicable.

4.3.5 Subgroup analyses

Not applicable.

4.4 SECONDARY ENDPOINT(S) ANALYSIS

4.4.1 Key/Confirmatory secondary endpoint(s)

The secondary endpoint of change in eGFR from the EFC15392 study baseline to 24 months of open-label extension study will not be analyzed.

Other secondary endpoints analyses are defined in Section 4.7.2 (AE, SAE).

4.4.1.1 Definition of endpoint(s)

4.4.1.2 Main analytical approach

Not applicable.

4.4.2 Supportive secondary endpoint(s)

Not applicable.

4.5 TERTIARY/EXPLORATORY ENDPOINT(S) ANALYSIS

4.5.1 Definition of endpoint(s)

Not applicable.

4.5.2 Main analytical approach

Not applicable.

4.6 MULTIPLICITY ISSUES

Not applicable.

4.7 SAFETY ANALYSES

All safety analyses will be essentially descriptive, and no testing is planned.

4.7.1 Extent of exposure

The extent of IMP exposure will be assessed by the duration of IMP exposure and summarized within the long-term safety population.

Duration of IMP exposure

Duration of LTS15823 IMP exposure is defined as last LTS15823 IMP administration date – first LTS15823 IMP administration date +1 day, regardless of unplanned intermittent discontinuations.

If the date of the last dose of IMP is missing, the duration of IMP will be left as missing.

Duration of IMP exposure will be summarized quantitatively and categorically:

- ≥1 day
- ≥1 Month
- ≥ 3 months
- >6 months

Additionally, the cumulative duration of treatment exposure (expressed in participant-years) will be provided.

4.7.2 Adverse events

General common rules for adverse events

All adverse events (AEs) will be coded to a lower-level term (LLT), preferred term (PT), high-level term (HLT), high-level group term (HLGT), and associated primary system organ class (SOC) using the Medical Dictionary for Regulatory Activities (MedDRA) version currently in effect at Sanofi at the time of database lock.

The AEs will be analyzed in the following 3 categories:

- Pre-treatment AEs: AEs that developed, worsened or became serious during the pre-treatment period.
- Treatment-emergent adverse events (TEAE)s: AEs that developed, worsened or became serious during the treatment-emergent period.
- Post-treatment AEs: AEs that developed, worsened or became serious during the post-treatment period.

Similarly, the deaths will be analyzed in the pre-treatment, treatment-emergent and post-treatment periods.

The AE reporting will be on TEAEs.

An AE with incomplete or missing date/time of onset (occurrence, worsening, or becoming serious) will be classified as a TEAE unless there is definitive information to determine it is a pretreatment or a post-treatment AE.

If the assessment of the relationship to IMP is missing for an AE, this AE will be assumed as related to IMP. If the severity is missing for 1 of the treatment-emergent occurrences of an AE, the severity will be imputed with the maximal severity of the other occurrences. If the severity is missing for all the occurrences, the severity will be left as missing.

Multiple occurrences of the same event in the same participant will be counted only once in the tables within a treatment phase.

The AE tables will be sorted as indicated in Table 4.

Table 4 - Sorting of AE tables

AE presentation	Sorting rules
SOC, HLGT, HLT and PT	By the internationally agreed SOC order and by alphabetic order of HLGTs, HLTs and PTs.
SOC and PT	By the internationally agreed SOC order and decreasing frequency of PTs ^{a, b}
[SMQ/CMQ] and PT	By decreasing frequency of [SMQs/CMQs] and PTs ^a

a Sorting will be based on the overall incidence

Analysis of all adverse events

The overview of TEAE with the details below will be generated:

- Any TEAE
- Any treatment emergent SAE
- TEAE leading to death
- Any TEAE leading to permanent intervention discontinuation
- Any treatment emergent AESI

The AE summaries of Table 5 will be generated with number (%) of participants experiencing at least one event.

Table 5 - Analyses of adverse events

Type of AE	MedDRA levels
All TEAE	Primary SOC, HGLT, HLT and PT
	Primary SOC and PT
TEAE related to IMP as per Investigator's judgment	Primary SOC and PT
TEAE by maximal intensity	Primary SOC and PT
Treatment emergent SAE	Primary SOC and PT
TEAE leading to permanent intervention discontinuation	Primary SOC and PT
TEAE leading to death (death as an outcome of the AE as reported by the Investigator in the AE page)	Primary SOC and PT
Treatment emergent AESI	Primary SOC and PT
Treatment emergent COVID-19 related AE	Primary SOC and PT

b The table of all TEAEs presented by SOC and PT will define the presentation order for all other tables (eg, treatment-emergent SAE) presented by SOC and PT, unless otherwise specified.

Analysis of deaths

In addition to the analyses of deaths included in Table 4 the number (%) of participants in the following categories will be provided:

- Deaths during the treatment-emergent and post-treatment periods by reason for death
- Deaths in non-enrolled participants or enrolled but not treated participants

Analysis of adverse events of special interest (AESIs) and other AEs of interest

Adverse events of special interest (AESIs) and other AEs of interest will be selected for analyses as indicated in Table 6. Number (%) of participants experiencing at least one event will be provided for each event of interest. Tables will be sorted as indicated in Table 4.

Table 6 - Selections for AESIs and other AEs of interest

AESIsand other AEs of interest]	Selection
Pregnancy of a female subject or female partner of a male subject	e-CRF specific pregnancy page
Symptomatic overdose (serious or non- serious) with IMP	e-CRF specific symptomatic overdose page
Increase in alanine transaminase (ALT)	e-CRF specific AESI tick box on the AE page
New or worsening lenticular opacities and cataracts	e-CRF specific AESI tick box on the AE page
AE related to COVID-19 illness	SMQ COVID19

4.7.3 Additional safety assessments

The analyses of additional safety assessments will not be done.

4.7.3.1 Laboratory variables, vital signs and electrocardiograms (ECGs)

Not applicable.

4.7.3.2 Neurological examination

Not applicable.

4.7.3.3 Ophtalomological examination

Not applicable.

4.7.3.4 Depression (BDI_II) examination

Not applicable.

4.8 OTHER ANALYSES

The analysis of the other parameters will not be done.

4.8.1 Pharmacodynamic analyses

Not applicable.

4.8.2 Patient reported outcomes analyses

Not applicable.

4.8.3 Biomarker analyses

Not applicable.

4.9 INTERIM ANALYSES

No interim analysis is planned.

5 SUPPORTING DOCUMENTATION

5.1 APPENDIX 1 LIST OF ABBREVIATIONS

AESIs: adverse events of special interest

ALT: Alanine transaminase HGLT: high level group term

IMP: Investigational medicinal product

MedDRA: medicinal dictionary for regulatory activities

PT: preferred term

SAP: statistical analysis plan SD: standard deviation SOC: system organ class

TEAE: treatment-emergent adverse event

5.2 APPENDIX 2 CHANGES TO PROTOCOL-PLANNED ANALYSES

This section summarizes major statistical changes in the protocol amendment(s).

Table 7 - Major statistical changes in protocol amendment(s)

Amendment Number	Approval Date	Changes	Rationale
1	16 Mar 2021	All participants will be treated for the duration of 24 months. The protocol instruction "or until venglustat is commercially available for patients, whichever comes first" is not applicable to the countries listed	To comply with the request raised during the EU VHP review phase, study participants in Belgium, Czech Republic, Denmark, Germany, Italy, Poland, Portugal, Romania, and Spain will receive venglustat (15 mg once daily) for the duration of 24 months

5.3 APPENDIX 3 DEMOGRAPHICS AND BASELINE CHARACTERISTICS, PRIOR OR CONCOMITANT MEDICATIONS

Demographics, baseline characteristics

The following demographics and baseline characteristics and disease characteristics at baseline will be summarized using descriptive statistics in the enrolled population.

Demographic and baseline characteristics

- Gender (Male, Female)
- Age in years (quantitative and categorical variable: <40, and ≥40 years) at the EFC15392 baseline as well as the LTS15823 baseline

- Race (White, Black or African American, Asian, American Indian or Alaska Native, Native Hawaiian or other Pacific Island, other)
- Ethnicity (Hispanic, non-Hispanic)
- Weight in kilograms (quantitative and categorical variable: <50, 50 to <100, ≥100) at the EFC15392 as well as the LTS15823 baseline

Disease characteristics

eGFR at EFC15392 screening, EFC15392 baseline and LTS15823 baseline (quantitative variable and qualitative variable: <30,30 to <45, 45 to <60, 60 to <75, 75 to <90, >=90) (see Section 5.4).

5.4 APPENDIX 4 DATA HANDLING CONVENTIONS

General conventions

The following formulas will be used for computation of parameters.

Demographic formulas

• BMI =
$$\frac{\text{weight(kg)}}{\text{height(m)}^2}$$

eGFR at EFC15392 screening

The screening eGFR is defined as the eGFR value that was selected to enroll the participant in the study:

- If eGFR at EFC15392 Visit 1 was between 45 and 89.9 mL/min/1.73 m² (or between 30 and 89.9 mL/min/1.73 m² for Stage 2), then the value at Visit 1 is considered as the screening value
- Else, if an additional eGFR measurement was done between EFC15392 Visit 1 and EFC15392 Visit 2, then this additional value is considered as the screening value
- Else, the eGFR at EFC15392 Visit 2 is considered as the screening value

Table 8 - eGFR values example

Subject	EFC15392 V1	EFC15392 Additional (between V1 and V2)	EFC15392 V2
1	87	ND	91
2	92	ND	85
3	95	86	93
4	92	95	88

eGFR at EFC15392 baseline

EFC15392 Baseline eGFR is defined for each participant as the average of eGFR values assessed prior or equal to 1st IMP in the EFC15392 study or prior or equal to randomization for randomized and not exposed participants.

eGFR at LTS15823 baseline

LTS15823 Baseline eGFR is defined:

- as the eGFR assessment performed at the time of EFC15392 V12 for each participant enrolled at the time of the EFC15392 V12.
- else, as the average of eGFR values assessed between LTS15823 screening visit up to 1st IMP in the LTS15823 (including) or prior or equal to enrollment for enrolled and not exposed participants.

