- Stage 1 (24 months of treatment): Randomized, double-blind, placebo-controlled, 3-arm study with primary objective to determine the effect of venglustat on the rate of TKV growth as compared to placebo in participants with eGFR between 45 and 89.9 mL/min/1.73 m² who are at risk of rapidly progressive ADPKD.
- Stage 2 (24 months of treatment): Randomized, double-blind, placebo-controlled, 2-arm study, with primary objective to determine the effect of venglustat on rate of renal function (eGFR) decline as compared to placebo in participants with eGFR between 30 and 89.9 mL/min/1.73 m² who are at risk of rapidly progressive ADPKD.

The seamless design of this 2-stage study is based on the similarities of the endpoints of the 2 stages and overlapping but not identical inclusion/exclusion criteria of the 2 stages.

More information on the safety of venglustat and on the clinical program can be found in the Investigator's Brochure (IB).

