1.2 OBJECTIVE AND ENDPOINTS

The Table 2 provides the objectives and endpoints as planned in protocol. Considering the decision to discontinue the study after enrollment of only 24 patients, statistical analyses of the study are revised and only demographic, baseline characteristics and adverse events will be summarized overall.

Table 2 - Objectives and endpoints

	Objectives	Endpoints
Prima	ry	
Secon	To determine the effect of early versus delayed treatment with venglustat on the total kidney volume (TKV) in participants at risk of rapidly progressive ADPKD.	 Percent change in TKV based on magnetic resonance imaging (MRI) from the EFC15392 study baseline to 24 months of open-label extension study, in early-treated and delayed-treated participants.
•	To determine the effect of early versus delayed treatment with venglustat on the renal function (estimated glomerular filtration rate [eGFR]).	 Change in eGFR (Chronic Kidney Disease Epidemiology Collaboration [CKD-EPI] equation) from the EFC15392 study baseline to 24 months of open-label extension study, in early-treated and delayed-treated participants.

Objectives Endpoints

- To characterize the safety profile of venglustat.
- To evaluate the effect of venglustat on the lens
- To evaluate the effect of venglustat on mood using Beck Depression Inventory-II (BDI-II).

by ophthalmological examination.

Tertiary

- To explore the impact of venglustat on total liver volume (TLV) (in participants with height adjusted TLV [htTLV] >2 L/m).
- To explore the effect of venglustat on systolic blood pressure (SBP) and diastolic blood pressure (DBP).
- To explore the effect of venglustat on type, frequency and dosage of analgesic/over the counter (OTC) pain medication administration.
- To explore the effect of venglustat on time to confirmed 30% and 40% reduction in eGFR.
- To explore the effect of venglustat on biomarkers associated with ADPKD (eg, Fibroblast Growth Factor 23 [FGF23], asymmetric dimethylarginine [ADMA]) (not applicable for Chinese participants).
- To explore the pharmacodynamic (PD) effects of venglustat by measuring downstream metabolites of glucosylceramide synthase (GCS) in plasma (not applicable for Chinese participants).
- To explore the effect of venglustat on pain (brief pain inventory short form [BPI-SF]), fatigue (Brief Fatigue Inventory [BFI]), and the EuroQoL 5dimension 5 level (EQ-5D-5L) score.

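### The SAP rule for EFC15392 screening eGFR puts no range check on the additional measurement, so read literally it returns 95 for Table 8 Subject 4, although only the Visit 2 value of 88 is in range

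*SAP*

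**What the plan says.** SAP 5.4 (Appendix 4) opens with the definition: "The screening eGFR is defined as the eGFR value that was selected to enroll the participant in the study". Three ordered steps follow.

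1. "If eGFR at EFC15392 Visit 1 was between 45 and 89.9 mL/min/1.73 m²", with the lower limit at 30 for Stage 2, the Visit 1 value is used.
2. Otherwise, "if an additional eGFR measurement was done between EFC15392 Visit 1 and EFC15392 Visit 2, then this additional value" is used. The only condition is that the measurement was done.
3. Otherwise, the Visit 2 value is used.

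The limits match those that Protocol 2.2.4 gives for the parent study: Stage 1 is described "as compared to placebo in participants with eGFR between 45 and 89.9" and Stage 2 "as compared to placebo in participants with eGFR between 30 and 89.9".

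Table 8 of the SAP lists four example subjects with their Visit 1, additional and Visit 2 values. In the text available it does not show which value is selected for each.

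The derived value is still needed. SAP 1.2 records the decision to "discontinue the study after enrollment of only 24 patients" and says that "only demographic, baseline characteristics and adverse events will be summarized overall". SAP 5.3 (Appendix 3) includes "eGFR at EFC15392 screening, EFC15392 baseline and LTS15823 baseline" among the disease characteristics, each summarized as a continuous variable and in categories with cut-points at 30, 45, 60, 75 and 90.

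**The concern.** The definition and the steps that implement it disagree. A value that enrolled a participant must lie in the entry range, and step 1 applies that test to Visit 1. Step 2 does not apply it to the additional measurement, and because the steps form an if/else chain, step 3 is reached only when no additional measurement was taken. A participant with Visit 1 out of range, the additional value out of range and Visit 2 in range is therefore given a value that could not have qualified them.

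Table 8 Subject 4 has exactly this pattern, so the gap shows up in the SAP's own example. The categories in SAP 5.3 have cut-points at 30, 45 and 90, on or next to the entry limits. An error of this kind can therefore put an enrolled participant in a category outside the parent study's entry range.

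**Working it through.** **Inputs.** Ranges: 45 to 89.9 (Stage 1) and 30 to 89.9 (Stage 2), from SAP 5.4 and Protocol 2.2.4. Example values: SAP Table 8 (ND = not done). Categories: SAP 5.3. Number enrolled: 24, from SAP 1.2. The SAP states no selected value for Table 8, so there is no figure of its own to reproduce.

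**Rule as written.** Use V1 if V1 is in range; else the additional value if it was done; else V2.

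**Rule with the check.** Use V1 if V1 is in range; else the additional value if it was done and is in range; else V2.

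| Subject | V1 | Additional | V2 | In-range value | As written | With check |
|---|---|---|---|---|---|---|
| 1 | 87 | ND | 91 | 87 | 87 | 87 |
| 2 | 92 | ND | 85 | 85 | 85 | 85 |
| 3 | 95 | 86 | 93 | 86 | 86 | 86 |
| 4 | 92 | 95 | 88 | 88 | **95** | **88** |

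The results are the same for both stages, because every out-of-range value in the table exceeds the common upper limit of 89.9. Each row has exactly one in-range value. The rule as written finds it for Subjects 1 to 3 and misses it for Subject 4.

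**Effect on the example.**
- Difference for Subject 4: 95 − 88 = 7 mL/min/1.73 m².
- Mean as written: (87 + 85 + 86 + 95)/4 = 353/4 = 88.25. With the check: (87 + 85 + 86 + 88)/4 = 346/4 = 86.5.
- Categories as written: three of four in 75 to <90 and one in ≥90. With the check: four of four in 75 to <90.

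**Lower limit (assumed values, for illustration).**
- Stage 1, values 44, 43, 46: as written 43 (30 to <45); with the check 46 (45 to <60).
- Stage 2, values 29, 28, 31: as written 28 (<30); with the check 31 (30 to <45).

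**Possible effect on the study table, per affected participant among 24.**
- Category percentage: 1/24 = 4.2 percentage points out of one category and into another.
- Mean, for an error the size of Subject 4's: 7/24 = 0.29 mL/min/1.73 m².

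**The case against.** The strongest reply is that SAP 5.4, read as a whole, already gives the right answer. The opening sentence governs, the steps only carry it out, and for Subject 4 neither 92 nor 95 could have enrolled the participant. Table 8 may also have marked the selected cell by formatting that does not survive in the extracted text. Both points bear on intent, and the intent is probably 88. Neither corrects the step: code written from the three conditions returns 95, and if the table does mark 88, it contradicts the step it illustrates.

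The second reply concerns impact, and it stands. The EFC15392 rules on repeat screening tests and the participant data are not in these documents, so the number affected is unknown and may be zero. The Table 8 means describe four illustrative subjects and are not study results. No inference depends on the value. The supplemental eGFR analysis in Protocol 9.3.3, which excluded participants with a screening value of 30 to 44.9, could have been affected, but SAP 4.4.1 drops the eGFR analysis.

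A third reply is that adding a check to step 2 still leaves step 3 unchecked. That is true but has little practical weight, since a participant with no in-range value should not have been enrolled.

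**Conclusion.** The concern holds as a minor error in a derivation rule. Step 2 conflicts with the SAP's own definition and gives 95 instead of 88 on one of its four examples. This rests only on the wording of SAP 5.4 and the ranges stated there and in Protocol 2.2.4.

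The consequence is limited to the screening eGFR row of the descriptive baseline table. LTS15823 eligibility does not use this rule, nor do the separate definitions of EFC15392 and LTS15823 baseline eGFR. The per-participant shifts shown above apply only if at least one of the 24 enrolled has the pattern, and the shift in the mean also assumes a 7-unit error. It has not been shown that any reported result would be wrong.

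**What to change.** Amend the second step in SAP 5.4 so that the additional measurement is used only if it lies within the participant's stage-specific range (45 to 89.9 for Stage 1, 30 to 89.9 for Stage 2), and otherwise the Visit 2 value is used. Add a column to Table 8 giving the selected values, and confirm that they are 87, 85, 86 and 88.

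The cost is one clause in the SAP and one condition in the derivation program. No new data are needed and no other analysis changes.
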